### 400 2.c Subject Recruitment Plans and Consent Process

401 Recruitment will be done at the Washington University Department of Otolaryngology-402 Head and Neck Surgery outpatient clinics. Advertisements will also be sent to all 403 members of the St. Louis ENT Club, and otolaryngologists whose practices are within 404 150 miles of Washington University Medical Center (WUMC). Direct recruitment of 405 potential participants will also be achieved through use of the Washington University 406 Volunteers for Health Research Participant Registry, and the Otolaryngology Research 407 Participant Registry. This recruitment strategy has been successful for two current trials 408 of treatment for COVID-associated anosmia VOLT (IRB ID# 202011046) and SCENT2 409 (IRB ID# 202101190). We may also attempt to recruit potential participants from past 410 studies in our lab, such as the CODS trial (IRB ID# 202004146). Additionally, due to the 411 focus on virtual research at this time, we may also use website postings and work with 412 anosmia support groups such as AbScent and FifthSense to share the trial.

### 413 2.d Randomization Method and Blinding

414 Participants who remain eligible at the end of the screening period will be randomized in 415 a double-blind fashion, according to a computer-generated random code, to receive either 416 placebo or gabapentin. [name] will provide the randomization table to the BJH 417 Research Pharmacist, who will prepare both gabapentin and placebo for the entire study. 418 The research assistants will collect the gabapentin and placebo in a blinded fashion from 419 the research pharmacist for distribution to the participants via FedEx.

### 420 **2.e Risks and Benefits**

The potential benefit to the participant is improvement of their olfactory dysfunction
using this therapy. The potential benefit to the society is the use of the pilot study results
to initiate a larger trial to further evaluate the efficacy of gabapentin in the treatment of
post-COVID-19 olfactory dysfunction.

425

The potential risk to participants during the study is an adverse event associated with the medication use. Abrupt cessation of gabapentin may alter the seizure threshold; for this reason, participants will be provided with a taper schedule specific to the gabapentin dose

429 at time of cessation. Gabapentin has a slight risk of dependence in individuals with

- 430 previous history of alcohol, cocaine, or opioid abuse so these individuals will be excluded
- 431 from the study. 17
- 432
- 433 The consent process informs a volunteer about the study, indicates that participation is
- 434 voluntary, and that he/she has the right to stop at any time. Risks are listed in the
- 435 informed consent form and described orally during the consent process.
- 436

### 437 **2.f Early Withdrawal of Subjects**

438 If a subject decides to withdraw from all components of the research study, the

439 investigator will discontinue all of the current and scheduled research activities in the

440 study. Participants taking an intervention medication at the time of withdrawal will be

441 provided with a taper-down schedule based on maximum intervention dose achieved.

442

### 443 **2.g** When and How to Withdraw Subjects

444 A participant can withdraw consent for the study at any time. Participants will be allowed 445 to end participation in the study at any point should they desire. If a participant must be 446 withdrawn due to a drug-related serious adverse event, then blind will be broken and, if 447 on gabapentin, drug withdrawal will be tapered or completely stopped based on the 448 clinical judgement of the PI. All participants will have an exit interview to ascertain any 449 adverse effects and discuss the reason for ending participation. The study team will 450 follow them for safety reasons up to 30 days after stopping use of the study drug.

451

### 452 **2.h Data Collection and Follow-up for Withdrawn Subjects**

453 If a participant has ended participation, the only data that will be collected are the data
454 from the exit interview and the data collected prior to withdrawal. There will not be any
455 other follow-up or data collected from these subjects.

456

457 Data collected up to this point will not be used in the analysis, and further data will not be458 collected from these participants.

459

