### 217 **Primary Outcome:**

218 Clinical Global Impression of Improvement Scale (CGI-I). The response rate is 219 defined as the number of participants self-reporting minimal change or larger on 220 the Clinical Global Impression of Improvement Scale (CGI-I) scale, divided by 221 the number of participants in each group. The CGI-Improvement is a self-222 reported scale of improvement ranging from 1 to 7 (1 is Very Much Improved, 7 223 is Very Much Worsened) and will be measured after completing 8 weeks of the 224 fixed, highest-tolerable dose. Each rating is well defined to maximize accuracy. 225 Participants reporting 3 as Minimally Improved, 2 as Much Improved, or 1 as Very 226 Much Improved in the CGI-I will be deemed responders to treatment, and the 227 number of responders to non-responders will be compared between the two arms -228 CGI-Severity (CGI-S) and CGI-Improvement (CGI-I).

229	
230	
231	Secondary Outcomes:
232	1. CGI-Severity. The CGI-Severity scale ranges from 1 to 7, where 1 is normal
233	function and 7 is complete anosmia. This assessment will provide subjective data
234	on patients' baseline olfactory function prior to beginning the trial, after 8-week
235	Fixed-Dose period, and 4 weeks after completion of Taper-Down phase.
236	2. CGI-Improvement. The CGI Improvement will also be administered 4 weeks
237	after completion of Taper-Down phase which same analysis as described above.
238	3. University of Pennsylvania Smell Identification Test (UPSIT).  The UPSIT is
239	composed of 40 strips of microencapsulated odorants, which are present on the
240	bottom of each page, just below a four-alternative multiple-choice question. For a
241	given item, the patient releases an odor by scratching the microencapsulated pad
242	with a pencil tip, smells the pad, and indicates the odor quality from four
243	alternatives. Even if no smell is perceived, a response is required (i.e., the test is
244	forced-choice). The subject's total correct score out of the 40 items is
245	determined. 
246	The total UPSIT score can range from 0 to 40 and scores are interpreted as the
247	level of absolute smell function (i.e., normosmia, mild hyposmia, moderate
248	hyposmia, severe hyposmia, and anosmia), using the age- and sex-related
249	normative classification system described in the UPSIT manual (Table 1) The
250	minimal clinically important difference in UPSIT score is 4.

Disease Classification Based on UPSIT		Women	Men

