### 814 G3 Statistical Methods

815 An intention-to-treat analysis will be used for the primary analysis of the data. All

816 participants will be examined in the groups to which they were initially assigned.

817 Standard descriptive statistics will be used to assess the demographics, clinical

818 characteristics, and olfactory test results of the study population. The difference in rate of

responders after Fixed-Dose period will estimate the effect size of the primary outcome

820 measure, and the 95% CI around that point estimate will measure precision. In each

group, the frequency and relative frequency of the participants' response to the global

rating of smell change will be reported for each Likert category. Fisher's exact test will

be used for comparing the responders' rates between the 2 groups. Histograms and

- 824 Shapiro-Wilks test will be used to test the normal distribution assumption of the
- 825 continuously measured UPSIT scores and the differences pre-post treatment in each of
- the groups. Independent samples t-test or its nonparametric equivalent Mann-Whitney U
- test will be used to compare the change in UPSIT scores between the two groups. Mixed
- 828 effects model will be used to test whether the change in UPSIT score from baseline to
- end of treatment is significantly different between 2 groups. Subjects will be treated asrandom factors, and group and time will be used as fixed factors in the model. Interaction
- of group by time will be explored. Effect sizes with 95% CIs will be reported for each
- analysis. All statistical analyses will be conducted in SPSS 28 (IBM Corp., Armonk,
- 833

NY).

834

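### Section 2.h bars use of data already collected from withdrawn participants, which contradicts the intention-to-treat primary analysis in G3 and leaves the CGI-I denominator unsettled

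*Combined protocol and SAP*

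**What the plan says.** **Analysis principle.** G3 (Statistical Methods) states: "An intention-to-treat analysis will be used for the primary analysis of the data". It adds that all "participants will be examined in the groups to which they were initially assigned".

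**Withdrawn participants.** Section 2.h (under E2) covers anyone who has ended participation. It first limits collection to the exit interview and what was gathered before withdrawal, and rules out any "other follow-up or data collected from these subjects". It then says: "Data collected up to this point will not be used in the analysis". Section 2.g, just before it, says that the team will "follow them for safety reasons up to 30 days after stopping use of the study drug".

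**Primary outcome.** C3 divides CGI-I responders by "the number of participants in each group", without saying whether that means randomised or evaluable. The rating "will be measured after completing 8 weeks of the" fixed dose. F2 and F3 then add a taper of up to 2 weeks and a follow-up of 4 weeks, within a maximum of 18 weeks.

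**Numbers and missing data.** G1 has 60 randomised, a 33% dropout rate, 40 evaluable cases and precision based on 20 per group. Section 3.c (under E3) gives 20 per group as the allocation. G4 assumes that missing data are missing at random and makes no adjustment for them.

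**The concern.** An analyst cannot keep everyone in the assigned group and also set aside data already obtained from those who left. No section gives either instruction precedence.

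For a participant who leaves before the end of the Fixed-Dose period there is no primary rating to discard, and the question is only how a missing value is counted. For one who leaves later, the primary rating exists and 2.h removes it. That is not missing data in the sense of G4. It is exclusion on an event after randomisation, which intention-to-treat is meant to prevent.

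Section 2.h is not limited to efficacy. Read literally, it also removes withdrawn participants' adverse-event data from the secondary aim (C2), which is to describe adverse effects. That also sits badly with F3, which says that an event leading to unblinding and removal will be described in the adverse-event report.

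The planned outputs are a difference in response rates, its 95% CI and a Fisher test. All three depend on who is counted, so the analysis set should be settled before the data are seen.

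**Working it through.** **Inputs from G1:** 60 randomised (30 per arm at 1:1), 33% dropout, placebo response 30%, target difference 25 points (so 55% on gabapentin), 20 evaluable per arm. **From F2 and F3:** taper at most 2 weeks, follow-up 4 weeks, maximum 18 weeks.

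**1. Reproduce the plan's figures.** 60 × (1 - 0.33) = 40.2, so 40 evaluable. Unpooled Wald interval: d ± 1.96 × √[p₁(1-p₁)/n + p₂(1-p₂)/n]. With 11/20 and 6/20: 0.25 ± 1.96 × √[(0.2475 + 0.21)/20] = 0.25 ± 0.296, or -4.6 to 54.6 points (Fisher p = 0.20). This rounds to the stated -5% to 55%. The arithmetic in G1 is correct, and its precision is that of 20 evaluable per arm.

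**2. Window in which 2.h removes an observed CGI-I.** 2 + 4 = 6 weeks at most. The longest listed taper is three 3-day steps, or 9 days, so on that schedule it is (9 + 28)/7 = 5.3 weeks.

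**3. How many people.** The documents do not say. If the 20 losses split equally, the range is 0 to 10 per arm. If they were also spread evenly over 18 weeks, 20 × 6/18 = 6.7, or about 3 per arm. Both the equal split and the even spread are assumptions.

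**4. Effect of restoring those ratings.** The base is 20 per arm.

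| Restored per arm | Assumed response in those restored | Difference (points) | 95% CI |
|---|---|---|---|
| 0 | not applicable | 25.0 | -4.6 to 54.6 |
| 3 | same rates, 55% v 30% | 25.0 | -2.6 to 52.6 |
| 10 | same rates, 55% v 30% | 25.0 | 0.8 to 49.2 |
| 3 | all placebo, no gabapentin (11/23 v 9/23) | 8.7 | -19.8 to 37.2 (p = 0.77) |
| 3 | all gabapentin, no placebo (14/23 v 6/23) | 34.8 | 8.0 to 61.6 (p = 0.036) |

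The last two rows are arithmetic bounds, not forecasts. The row with 10 per arm needs every planned loss to come after the Fixed-Dose survey.

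**5. The separate question of the denominator.** With the same responders over all randomised, and everyone lost counted as a non-responder, 11/30 - 6/30 = 16.7 points (-5.7 to 39.1; p = 0.25), against 25.0 over 20 per arm. With unequal loss (assumed: 16 gabapentin and 24 placebo evaluable), 9/16 - 7/24 = 27.1 points, but 9/30 - 7/30 = 6.7. These figures show why the counting rule must be written down. They do not measure the 2.h sentence, because deleting that sentence would not turn 25.0 into 16.7.

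**The case against.** The strongest reply is that the trial is a pilot sized on feasibility, that G4 already implies an analysis of available ratings, and that 2.h may affect nobody. If all 20 losses come before the Fixed-Dose survey, no primary rating is discarded. At equal response rates, restoring 3 per arm hardly moves the interval. Section 2.h may also have been written to respect withdrawn consent.

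Much of this stands. The numerical effect rests on an assumed timing of dropout and may be zero. The contradiction remains, because G4 addresses missing data and does not say whether ratings that were obtained and then set aside count as missing. Nor is 2.h confined to withdrawn consent: it applies to anyone who has ended participation, and F3 also removes participants for serious adverse events.

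Three stronger readings are tempting, and the documents do not support them.

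- A reader might infer that 2.h costs 8.3 points (25.0 to 16.7). That shift needs every dropout to be counted as a non-responder, a rule that no section prescribes and that G4 points away from.
- A reader might take the 20 per group in 3.c to mean that only 40 are randomised. G1 says plainly that 60 are randomised, and 20 per group matches its evaluable number. This is a drafting mismatch.
- A reader might infer a bias in favour of gabapentin. The documents say nothing about when or why people would leave each arm, so any bias could be zero or go either way.

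**Conclusion.** The point holds in a narrow form. G3 and 2.h contradict each other on who enters the primary analysis, and C3 names a denominator without fixing it. The correction is needed because of the contradiction in the text, not because of a demonstrated bias.

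The number of observed CGI-I ratings at risk is unknown: 0 to 10 per arm under an equal split of the planned 20 losses. At 3 per arm and unchanged response rates the point estimate stays at 25.0 and the interval narrows by 2.0 points at each end. Only an extreme pattern, or the top of the range, gives an interval that excludes zero. The sample-size arithmetic in G1 is not in question.

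**What to change.** 1. In 2.h, delete the sentence that excludes collected data. State that all data collected before withdrawal, including every CGI-I obtained and all adverse-event data, are analysed as randomised, subject to the consent terms.
2. In C3 and G3, define the primary denominator as all randomised participants with a CGI-I rating, analysed in the assigned group. This agrees with the no-adjustment rule in G4 and the 40 evaluable cases in G1.
3. Add a sensitivity analysis that counts a missing CGI-I as non-response over all randomised, with dropout counts and reasons by arm. Fix both rules before unblinding.
4. Reconcile the bar on other follow-up in 2.h with the 30-day safety follow-up in 2.g, and the 20 per group in 3.c with the 60 randomised in G1.

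The cost is a few sentences and one extra table. The drawbacks are that the reported difference may look smaller and that missing as non-response can itself mislead when dropout differs between arms. That is why it is proposed as a sensitivity analysis, reported beside the dropout counts.

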### 587 Gabapentin (300 mg pill) Titration Schedule

588

586

589 If at any point during the Titration Period, the participant wishes to discontinue 590 the medication for any reason, they will be instructed to follow the taper down schedule 591 (see below) in order to safely stop the medication. The participant will be informed that 592 any abrupt stoppage of gabapentin could cause serious adverse effects.

Participants will be contacted by telephone or video call by the Research Assistant
(RA) at the end of Titration period. The purpose of this call will be to query the
participants about adverse effects. Participants will be provided with a paper calendar
and asked to maintain diaries of olfactory and taste symptoms and adverse effects
possibly related to the intervention.

598 Participants will not complete any forms at the completion of Titration period.599 Instead, they will proceed directly to Fixed-Dose Period.

### 600 601

Fixed-Dose Period: duration 8 weeks

602During the Fixed-Dose period, participant's dose will remain at their maximum tolerated603dosage established during the Titration phase. The study drug will be distributed in eight604separate vials representing the eight weeks of the Fixed-Dose period. The RA will605contact the participants at the end of Week 4 to administer the blind assessment using606REDCap (survey titled: "Blind Assessment"). Participants will complete the following607forms after completing the Fixed-Dose Period (survey titled: "FixedDoseSurvey"):

- 608
- 609 1.) Clinical Global Impression of Severity Scale (CGI-S).

610 2.) Clinical Global Impression of Improvement Scale (CGI-I)

- 611 3.) University of Pennsylvania Smell Identification Test (UPSIT)
- 612 4.) Olfactory Dysfunction Outcomes Rating (ODOR)
- 613 5.) *NASAL-7*
- 6.) *Clinical Global Impression-Severity Scale for Parosmics (CGI-P)*
- 615 7.) Adverse Event assessment
- 616 8.) Compliance
- 617

618 *Adverse events*. Any unintentional or unfavorable clinical sign or symptom, any new

619 illness or disease or the deterioration of existing disease or illness, or any clinically

620 significant deterioration in any laboratory assessments or clinical tests while participating

621 in this study will be captured. The study coordinator will contact participants virtually to

622 answer questions and assess adverse effects after Titration period, Fixed-Dose period,

- 623 and 4 weeks after Taper.
- 624

- 625 Taper Down: maximum duration 2 weeks

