- 626 Upon completion of the Fixed-Dose period, all participants in the study will be
- 627 titrated off study drug through a taper down period of maximum 2 weeks. Taper schedule
- 628 will directly relate to maximum gabapentin dose achieved during trial and is described in
- the Table below. The study drug will be distributed in 2 separate vials representing eachof the two weeks of the Taper-Down Period. It should be noted, participants randomized
- to placebo will also receive sufficient capsules to complete a taper down. In this way, the
- 632 blind will be maintained.

AT 3600 MG	AT 2700 MG	AT 1800 MG	AT 900 MG
FOR 3 DAYS 3 MORNING 3 NOON 3 NIGHT	FOR 3 DAYS 2 MORNING 2 NOON 2 NIGHT	FOR 3 DAYS 1 MORNING 1 NOON 1 NIGHT THEN STOP	NO TAPER REQUIRED
NEXT 3 DAYS 2 MORNING 2 NOON 2 NIGHT	NEXT 3 DAYS 1 MORNING 1 NOON 1 NIGHT THEN STOP		
FINAL 3 DAYS 1 MORNING 1 NOON 1 NIGHT THEN STOP			

634 Gabapentin Taper Down Schedule

635

635	
636	End of Study Intervention: Exit Interview/ Data Collection: 4 weeks after
637	completing Taper Down
638	The RA will contact the participants to query participants about compliance
639	with taper-down schedule and maintenance of diaries. Participants will complete the
640	following forms (survey titled: "FinalSurvey"):
641	1. Clinical Global Impression of Severity Scale (CGI-S).
642	2. Clinical Global Impression of Improvement Scale (CGI-I)
643	3. University of Pennsylvania Smell Identification Test (UPSIT)
644	4. Olfactory Dysfunction Outcomes Rating (ODOR)
645	5. NASAL-7
646	6. Clinical Global Impression-Severity Scale for Parosmics (CGI-P)
647	
(10	
648	F3 Safety and Adverse Events
649	
650	3.a Safety and Compliance Monitoring
	v I O

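### Section 2.h cancels the 30-day safety follow-up promised in 2.g and bars withdrawn participants' data from the analysis without exempting adverse events

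*Combined protocol and SAP*

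**What the plan says.** Section E2 2.g deals with participants who end participation. Each has an exit interview to establish any "adverse effects and discuss the reason for ending participation", and the team will "follow them for safety reasons up to 30 days after stopping use of the study drug".

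Section E2 2.h deals with the same people. It limits data collection to the exit interview and what was gathered before withdrawal, and says there will be no "other follow-up or data collected from these subjects". It then states: "Data collected up to this point will not be used in the analysis". The same sentence repeats that nothing further will be collected.

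Under E2 2.f, a participant who withdraws while on study medication is "provided with a taper-down schedule based on maximum intervention dose achieved".

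C2 makes the description of gabapentin's adverse effects the secondary aim. G3 sets out the efficacy analyses but gives no adverse-event summary and no safety population. Section J promises a discussion of adverse effects, without a tabulation.

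**The concern.** Two things are wrong in one short section.

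First, 2.g and 2.h give opposite instructions on following participants after they stop. Some of those who withdraw are still taking study drug during the taper. The protocol itself warns that abrupt cessation may affect the seizure threshold (D3) and may cause serious adverse effects (F2, Titration Period). A note to the F2 flow chart also requires reporting of deaths and of unanticipated or life-threatening events within 30 days of active participation. Staff who follow 2.h could miss events in that window.

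Second, the exclusion from the analysis is unqualified. If it is applied to adverse events, the by-arm summary describes only participants who did not withdraw. Non-serious events that led someone to leave would be recorded and then left out of the summary. The resulting rates are too low if those who withdrew had more events than those who stayed, unchanged if the rates were equal, and too high if they had fewer.

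**Working it through.** **The two rules side by side**

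| Question | 2.g | 2.h |
|---|---|---|
| Who is covered? | Participants who end participation | Participants who have ended participation |
| Follow-up after stopping drug | Up to 30 days, for safety | None beyond the exit interview |
| Adverse effects asked about at exit? | Yes | Exit-interview data are collected |
| Use of the data | Not addressed | Excluded from the analysis, with no exception |

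The populations are the same and the follow-up rules are incompatible. On use of the data, the only text that could override 2.h would be an adverse-event analysis in G3, and there is none.

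**Length of follow-up in dispute**

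Inputs: the 30 days in 2.g and the F2 taper table, whose longest schedule ends with "FINAL 3 DAYS 1 MORNING 1 NOON 1 NIGHT THEN STOP". Taper length is set by the maximum dose achieved.

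Follow-up after the withdrawal decision = taper days + 30:

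- 900 mg/d: 0 + 30 = 30 days
- 1800 mg/d: 3 + 30 = 33 days
- 2700 mg/d: 6 + 30 = 36 days
- 3600 mg/d: 9 + 30 = 39 days

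These are upper limits, because 2.g says up to 30 days. Under 2.h the figure is whatever the exit interview covers. Its timing for someone who withdraws is not stated; F2 uses the same term for the contact four weeks after taper.

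**How many participants could be left out**

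Inputs from G1: 60 enrolled, 33% dropout, 40 evaluable. The plan's own figure reproduces: 60 × (1 − 0.33) = 40.2, about 40. Dropouts: 60 × 0.33 = 19.8, about 20, which agrees with 60 − 40 = 20.

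With 60 randomised 1:1 there are 30 per arm. The share of an arm left out is d/30 for d dropouts. The documents do not give the split by arm; the splits below are assumptions.

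- 10 and 10: 10/30 = 33% of each arm
- 14 and 6: 14/30 = 47% of one arm, 6/30 = 20% of the other

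**Effect on an adverse-event rate**

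Understatement of an arm's rate = (d/30) × (rate in dropouts − rate in completers). The rate differences below are assumptions used only to show the range; a negative result means the rate is overstated.

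| Dropouts in arm | −20 points | 0 | +20 points | +40 points |
|---|---|---|---|---|
| 6 | −4.0 | 0 | 4.0 | 8.0 |
| 10 | −6.7 | 0 | 6.7 | 13.3 |
| 14 | −9.3 | 0 | 9.3 | 18.7 |

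A worked case with assumed counts: 30 on gabapentin, 10 withdrawn, and 4 of the 20 completers with an event. The completers-only rate is 4/20 = 20%. Including everyone, it is 4/30 = 13% if none of the 10 had an event, 9/30 = 30% if five did, and 14/30 = 47% if all did.

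**The case against.** The best defence is that 2.h was never meant to reach safety. The only analysis described in G3 is of efficacy, so the analysis in 2.h may mean efficacy alone. Adverse events have their own route. F2 captures them broadly during participation ("Any unintentional or unfavorable clinical sign or symptom, any new" and more), F3 3.c collects them from source and F3 3.e sends them to the IRB. F3 (Medical Monitoring) puts serious or unexpected events that require unblinding into an adverse-event report. It would be odd to hold an exit interview about adverse effects and then discard the answers. On this view 2.h limits research follow-up, while 2.g governs safety contact.

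That reading is possible, but no sentence says so, and 2.h states twice that collection ends. Capture and IRB reporting do not amount to a summary by arm. The protected report covers only serious or unexpected events in which the blind has to be broken, so an ordinary event that leads to withdrawal has no such protection.

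Several limits do stand:

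- Stopping or reducing drug is not stated to be the same as ending participation, so 2.h reaches only those who end participation.
- The figure of 20 is planned dropout, and some of these participants may be non-evaluable without having withdrawn.
- The taper table does not list intermediate doses such as 2400 mg/d, which F2 allows, and after a drug-related serious event 2.g permits stopping with no taper.
- A safety population and a separate display of withdrawals are good practice; the contradiction does not depend on them.

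It is also fair to say that the same sentence of 2.h sits badly with the intention-to-treat statement in G3. That is a further reason to rewrite it, and it does not weaken this point.

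**Conclusion.** The concern holds. As written, 2.h cancels safety follow-up that 2.g promises, for up to 30 to 39 days after a decision to withdraw. It also excludes withdrawn participants' data without exempting adverse events, against the stated secondary aim. On the planned dropout, about 20 of 60 participants could be affected. This assumes that dropout means formal withdrawal and that 2.h is applied to the adverse-event summary. The bias in adverse-event rates cannot be sized or signed from the documents. Serious events are largely covered by other provisions; the gap is mainly in non-serious events that end in withdrawal and in events after drug is stopped. This should be corrected, because following the text as it stands gives the wrong result.

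**What to change.** - In 2.h, state that the exclusion does not apply to safety data. Adverse events recorded before withdrawal, at the exit interview and during the 30-day follow-up are all analysed.
- Remove the two statements in 2.h that end follow-up and data collection, and refer to the 30-day rule in 2.g. Make an exception for participants who refuse further contact, which fits the case in 2.f of withdrawal from all components of the study.
- In G3, add an adverse-event summary by arm. Preferably base it on everyone who took at least one dose and show withdrawals due to adverse events separately.

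The cost is a few sentences and one table. The exit interview and 30-day follow-up are already in 2.g, so no new visits are needed.
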